exercise session (e.g., improved mood, feeling energized, feeling accomplished/proud, or feeling good about doing something beneficial for the body). They then shared their responses with the interventionist and participants were encouraged to think about these positive experiences, feelings, and motivations for engaging in exercise often, and specifically during the next exercise session.

Post-intervention assessment

Non-exercisers in both arms were informed they could increase their PA following Exercise Session 2 if they desired, and they were given the Sensewear armband to wear for 1 week to objectively assess whether there was an intervention effect on bout-related MVPA. Further, during the week following Exercise Session 2, all non-exercisers were asked to complete recalled affect questionnaires for Exercise Session 2 at 1, 3, and 7 days following the session, as was done previously.

Exercise Session 3

One to two weeks following Exercise Session 2, non-exercisers from both the control and intervention groups returned to the laboratory for a third exercise session (Exercise Session 3). This session was identical to the previous exercise sessions and measures of anticipated affect, pre-, during, and post-exercise affect were obtained. All non-exercisers attending Exercise Session 3 (INT and CON) were compensated \$50 for their time.

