## **Statistical analysis**

Preliminary analyses were conducted to compare the groups (exercisers vs. non-exercisers) with respect to demographic variables including age, BMI, and gender. Chi Square tests were used to assess between-group differences in categorical variables and independent two-sample t-tests were used for continuous variables. First, unadjusted between-group differences in anticipated affect, pre-exercise affect, and post-exercise affect were assessed using independent two-sample t-tests. Next, using a series of longitudinal linear mixed effects models, we examined between-group (exercisers vs. non-exercisers) differences in serial measures of during-exercise affect (5, 10, 15, 20, 25 minutes) and post-exercise affect (immediate and 15 minutes post-exercise). Models included a subject-specific intercept and adjusted for repeated measures within participant over time. A similar analytic strategy was used to examine group differences in recalled affect (1, 3, and 7 days post-exercise). The goal was to determine the degree to which global recalled affect is associated with (i.e., biased toward) affective responses during or after PA and whether this differs between exercisers and non-exercisers. Correlation analysis was used to examine whether affective recall bias was correlated with anticipated affect towards future exercise. Finally, between-subjects ANOVAs were used to compare non-exercisers receiving the brief cognitive intervention to those in the control group on anticipated affect, affective response to exercise session 3, recalled affect for exercise session 2, and minutes/week spent in MVPA (assessed via the armband). All analyses were carried out in SAS 9.3 with significance level set at .05 a priori. Mixed effects models use a likelihood based approach to estimation, thus making use of all available data without directly imputing missing value.

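### The INT versus CON ANOVAs leave the outcome value and missing data undefined and make no use of the Session 1 and 2 ratings, while the likelihood mixed models serve only the non-randomised comparison

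*SAP*

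**What the plan says.** The SAP (Statistical analysis) handles the two comparisons differently.

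- **Exercisers versus non-exercisers, serial outcomes.** The SAP states "using a series of longitudinal linear mixed effects models, we examined between-group (exercisers vs. non-exercisers) differences in serial measures of during-exercise affect", together with the two post-exercise ratings. For recall: "A similar analytic strategy was used to examine group differences in recalled affect (1, 3, and 7 days post-exercise". These models have a subject-specific intercept.
- **INT versus CON.** Here "between-subjects ANOVAs were used to compare non-exercisers receiving the brief cognitive intervention to those in the control group". The outcomes are Session 3 affect, Session 2 recall, armband MVPA and anticipated affect. No covariate, analysis population, outcome construction or missing-data rule is given.
- **Missing data.** The one statement in the SAP text available concerns the mixed models, "thus making use of all available data without directly imputing missing value". It does not mention the ANOVAs.

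The randomised data are also repeated. Under Post-intervention assessment the Protocol has non-exercisers "complete recalled affect questionnaires for Exercise Session 2 at 1, 3, and 7 days following the session". Under Exercise Session 3 it says that the visit repeats the earlier sessions, so there are Feeling Scale ratings every 5 minutes and two afterwards. Sessions 1 and 2 gave the same ratings before randomisation, which follows Session 2.

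**The concern.** A between-subjects ANOVA has no within-person factor, so each participant enters with one value per outcome. Someone without that value is left out unless it is imputed, and no imputation is planned. The Session 3 outcomes depend on a return visit one to two weeks after Session 2, and recall depends on unsupervised online questionnaires. The Protocol describes payment by attendance ("All non-exercisers attending Exercise Session 3 (INT and CON) were compensated") and gives no attendance figure.

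Two things are at stake. First, if return to Session 3 depends on how earlier exercise felt, and does so differently by arm, an attenders-only comparison is no longer protected by randomisation. Second, each participant's Session 1 and 2 ratings probably predict Session 3, and the planned analysis ignores them. With 15 per arm that is expensive: a two-sided 0.05 t-test has 80% power only for a difference of about 1.06 SD, even with all 30 observed.

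**Working it through.** The documents state no power, SD, correlation or dropout rate, so there is no figure of the plan's own to reproduce. From the documents: 15 per arm (Protocol, Randomized Controlled Trial for Non-Exercisers), three recall prompts, three sessions, alpha 0.05 (two-sided assumed). Miss rates, correlations and dropout mechanisms below are assumptions. Outcomes are scaled to SD 1.

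**1. Session 2 recall.** Let m be the chance of missing a prompt, independent across prompts, with exchangeable correlation ρ.

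- All three answered: (1 − m)³. For m = 0.05, 0.10, 0.20 this is 0.857, 0.729, 0.512, or 12.9, 10.9, 7.7 of 15 per arm.
- At least one answered: 1 − m³. Of 30, this keeps 29.97 at m = 0.10 and 29.76 at m = 0.20.
- Complete-case variance of the arm difference is proportional to [(1 + 2ρ)/3]/(1 − m)³. The likelihood variance comes from inverting the information matrix averaged over missing-data patterns. The SE ratio at ρ = 0.5 is 1.07, 1.15, 1.34.

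Simulated SE of the INT − CON difference (4,000 runs, 15 per arm, missing completely at random):

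| Value used | ρ 0.5, m 0.10 | ρ 0.5, m 0.20 | ρ 0.7, m 0.10 | ρ 0.7, m 0.20 |
|---|---|---|---|---|
| Mean, all three required | 0.348 | 0.433 | 0.383 | 0.474 |
| Day 7 only | 0.381 | 0.412 | 0.381 | 0.410 |
| Mean of available prompts | 0.300 | 0.310 | 0.323 | 0.338 |
| Mixed model | 0.300 | 0.308 | 0.322 | 0.338 |

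So the loss depends on a choice that the SAP leaves open. The simulated ratio at ρ = 0.5, m = 0.20 (0.433/0.308 = 1.41) exceeds 1.34 because the number of completers per arm is small and varies by chance.

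**2. Session 3 precision.** With Sessions 1 and 2 as pre-randomisation outcomes and equal correlation ρ, the SE is multiplied by √[1 − 2ρ²/(1 + ρ)].

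- ρ = 0.5: √(1 − 0.5/1.5) = 0.816, about 18% lower.
- ρ = 0.7: √(1 − 0.98/1.7) = 0.651, about 35% lower.

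Simulation with 10% and 20% missing Session 3 agrees: 0.385 to 0.314 and 0.408 to 0.335 at ρ = 0.5; 0.392 to 0.255 and 0.417 to 0.271 at ρ = 0.7. The variance parameters were treated as known, so the gain in practice would be somewhat smaller. Deleting non-attenders from the model leaves the SE unchanged to three decimals. The precision gain is therefore baseline information, not retention.

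**3. Session 3 bias.** Assume no true effect, 20% dropout in CON only, and log-odds of dropout rising by 1 per SD of lower Session 2 affect. The CON attenders' mean is then too high by about 0.09 SD (Session 2 to 3 correlation 0.5) to 0.12 SD (0.7), and INT − CON is too low by that amount. With Session 2 in the model the bias is about zero.

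**4. Which model.** Extending the SAP's subject-intercept model to several sessions treats ratings within a session as no more alike than ratings across sessions. I took three sessions, five ratings each, 15 per arm, subject variance 50% of the total and no true effect. The test of arm on the change from Sessions 1 and 2 to Session 3, at nominal 5%, rejects about 16% of the time when session variance is 10% of the total and about 26% when it is 20%.

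**The case against.** The strongest reply is that the SAP never says that incomplete recall responders are dropped. A reader might infer that from the word ANOVA, but the text fixes only that there is one value per person. If that value is the mean of available prompts, almost nobody is lost and the SE matches the mixed model. This stands, and the 7/15/34% figures hold only if all three recalls are required. What remains for recall is that the rule is undefined, and that averages over different days mix time points if recall drifts.

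A reader might also infer that missing Session 3 removes a person from the whole randomised comparison, or that any mixed model would recover that person. Neither is supported. Session 2 recall and armband MVPA are collected in the week after Session 2, and a model on Session 3 data alone recovers nobody.

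The bias scenario is chosen, not observed. At 0.09 to 0.12 SD it is only about 0.22 to 0.31 of the SE of the difference (0.09/0.408 to 0.12/0.385). It disappears because dropout was made to depend on Session 2 affect alone. That too stands.

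Finally, the asymmetry is partial. In the observational comparison, "unadjusted between-group differences in anticipated affect, pre-exercise affect, and post-exercise affect were assessed using independent two-sample t-tests". Anticipated affect and weekly MVPA are not serial within a session or week, the randomised part is described as a pilot, and the SAP does not claim the all-available-data property for the ANOVAs. So there is no contradiction. A better analysis of data already being collected is still available for the one randomised contrast, which is tested at 0.05.

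**Conclusion.** The point holds in a limited form. The INT versus CON ANOVAs have no defined outcome value or missing-data handling, and they ignore pre-randomisation ratings held on every randomised participant. The firmest cost is precision at Session 3: an SE about 18% to 35% larger than needs be, relative to the ANOVA's own SE, for session correlations of 0.5 to 0.7. That cost arises even with full attendance. Protection against selective non-return is a secondary benefit, worth about 0.09 to 0.12 SD under one assumed mechanism. For recall the cost runs from almost none to about a third in SE, depending on an unstated rule. Actual missingness is unknown, so the documents do not support a claim that participants were in fact lost or the result biased. The statement about missing-data rules is limited to the SAP text available.

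**What to change.** - **(a) Session 2 recall.** Analyse days 1, 3 and 7 in a mixed model with arm, day and a subject intercept, using every available prompt.
- **(b) Session 3 during- and post-exercise affect.** Analyse by assigned arm in a likelihood model that includes the Session 1 and 2 values as pre-randomisation outcomes. Use per-session means or a session-within-subject random effect, not a subject intercept alone. Use Kenward-Roger degrees of freedom.
- **(c) Reporting.** Give the number with data per arm at each time point.

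The cost is SAP wording and a few more model runs, with no new data. The downside is a little more modelling, and reliance on a missing-at-random assumption and a covariance structure estimated from 15 per arm.
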